## List of abbreviations

---

ACQ-IA	Interviewer-administered Asthma Control Questionnaire
AE	Adverse Event
ALT	Alanine Aminotransferase
AST	Aspartate Aminotransferase
ATS	American Thoracic Society
b.i.d.	twice a day
BMI	Body Mass Index
BUN	Blood Urea Nitrogen
CFR	US Code of Federal Regulations
CHMP	Committee for Medicinal Products for Human Use
COPD	Chronic Obstructive Pulmonary Disease
CPO	Country Pharma Organization
CRF	Case Report/Record Form (paper or electronic)
CRO	Contract Research Organization
DAR	Dose administration record
DPI	Dry powder inhaler
DS&E	Drug Safety & Epidemiology
ECG	Electrocardiogram
EDC	Electronic Data Capture
e-Diary	Electronic Diary
EOT	End of Treatment
ERS	European Respiratory Society
FAS	Full Analysis Set
FDA	Food and Drug Administration
FEV 1	Forced Expiratory Volume in 1 Second
FVC	Forced Vital Capacity
GCP	Good Clinical Practice
GINA	Global Initiative for Asthma
GTL	Global Trial Leader
IB	Investigator Brochure
ICH	International Conference on Harmonization of Technical Requirements for Registration of Pharmaceuticals for Human Use
ICS	Inhaled Corticosteroid
IEC	Independent Ethics Committee
IRB	Institutional Review Board
IRT	Interactive Response Technology
IUD	Intrauterine device
IUS	Intrauterine System
LABA	Long Acting Beta-2 Agonist
LAMA	Long Acting Muscarinic Antagonist

---

---

LFT	Liver function test
LTRA	Leukotriene Receptor Antagonist
MAP	Master analysis plan
MDDPI	Multi dose dry powder inhaler
MDI	Metered-dose inhaler
MedDRA	Medical dictionary for regulatory activities
OC/RDC	Oracle Clinical/Remote Data Capture
o.d.	once a day
PDCO	EU Pediatric Committee
PEF	Peak Expiratory Flow
PK	Pharmacokinetic
PPS	Per Protocol Set
PRO	Patient Reported Outcome
QTc	Corrected QT interval
RAN	Randomized Set
SABA	Short Acting Beta-2 Agonist
SAE	Serious Adverse Event
SAMA	Short Acting Anticholinergics
SAP	Statistical Analysis Plan
SCS	Systemic Corticosteroids
SDDPI	Single Dose Dry Powder Inhaler
SGPT	Serum Glutamic Pyruvic Transaminase
SUSAR	Suspected Unexpected Serious Adverse Reactions
TD	Study Treatment Discontinuation
WHO	World Health Organization
WoC	Withdrawal of Consent

---

## Glossary of terms

Cohort	A specific group of patients/subjects fulfilling certain criteria
Control drug	Drugs(s) used as a comparator to reduce assessment bias, preserve blinding of investigational drug, assess internal study validity, and/or evaluate comparative effects of the investigational drug
Dosage	Dose of the study treatment given to the patient in a time unit (e.g. 100 mg once a day, 75 mg twice a day)
Enrollment	Point/time of patient entry into the study at which informed consent must be obtained (e.g. prior to starting any of the procedures described in the protocol)
Epoch	A portion of the study which serves a specific purpose. Typical epochs are: screening/recruitment, wash-out, treatment, and Follow-up
Investigational drug	The drug whose properties are being tested in the study; this definition is consistent with US CFR 21 Section 312.3 and is synonymous with “investigational new drug” or “investigational medicinal product.”
Medication pack number	A unique identifier on the label of each investigational drug package
Part	A single component of a study which contains different objectives or populations within that single study. Common parts within a study are: a single dose part and a multiple dose part, or a part in patients/subjects with established disease and in those with newly-diagnosed disease.
Patient/subject ID	A unique number assigned to each patient upon signing the informed consent
Randomization number	A unique identifier assigned to each randomized patient, corresponding to a specific treatment arm assignment
Study drug/ treatment	Any single drug or combination of drugs administered to the patient as part of the required study procedures; includes investigational drug(s), placebo/comparator active drug Run-in or background therapy
Study Treatment Discontinuation (TD)	When the patient permanently stops taking study treatment prior to the defined study treatment completion date
Variable	A measured value or assessed response that is determined in specific assessments and used in data analysis to evaluate the drug being tested in the study
Withdrawal of consent (WoC)	Withdrawal of consent from the study is defined as when a patient does not want to participate in the study any longer, and does not want any further visits or assessments, and does not want any further study related contact, and does not allow analysis of already obtained biologic material

## Protocol summary

Protocol number	QMF149G2202
Title	A multicenter, randomized, double-blind, active-controlled, 2 week treatment, parallel-group study to assess the efficacy and safety of indacaterol acetate delivered via the Concept1 inhalation device in children greater or equal to 6 and less than 12 years of age with asthma
Brief title	Efficacy and safety of indacaterol acetate delivered via the Concept1 inhalation device in children greater or equal to 6 and less than 12 years of age with asthma
Sponsor and Clinical Phase	Novartis Phase II
Investigation type	Drug and Concept1 Device (Breezhaler®)
Study type	Interventional
Purpose and rationale	This study is designed to explore lung function effects of two doses of indacaterol acetate, 75 µg and 150 µg, in pediatric asthma patients, and to compare the systemic exposure to indacaterol in plasma with historical data in adults, to identify an appropriate dose for Phase III evaluation.
Primary Objective(s)	The primary objective of this study is to evaluate indacaterol acetate 75 µg o.d and 150 µg o.d. in terms of change from baseline in pre-dose trough FEV 1 after 2 weeks of treatment.
Secondary Objectives	One secondary objective is to evaluate the systemic exposure to indacaterol in plasma following sparse pharmacokinetic (PK) sampling on Day 1 and Day 14 after oral inhalation of indacaterol acetate 75 µg and 150 µg. Other secondary objectives include the evaluation of clinical effects and pharmacodynamics of indacaterol acetate (75 µg and 150 µg o.d.) after 2 weeks of treatment in terms of: ACQ-IA score, lung function parameters, rescue medication usage and symptoms as recorded by patient e-diary. Safety (including labs, vital signs, ECG, adverse events), and tolerability of indacaterol acetate (75 and 150 µg o.d.) over 2 weeks of treatment will be evaluated.
Study design	A multicenter, randomized, double-blind, active-controlled, 2 week treatment, parallel-group study
Population	The study population will consist of approximately 80 male and female children ≥ 6 years and < 12 years with persistent asthma
Key Inclusion criteria	1. Male and female children ≥ 6 years and < 12 years with confirmed diagnosis of asthma for at least 1 year prior to study

	
enrollment.
 

2. Written informed consent by parent(s)/legal guardian(s) and depending upon their age and local requirements a consent or assent for the patient.

3. Patients receiving daily treatment with a stable low dose Inhaled Corticosteroid (ICS) (with or without additional controller), or patients receiving daily treatment with a stable mid-dose ICS (monotherapy or together with LTRA) for at least 4 weeks prior to Screening, and able to tolerate fluticasone propionate 100 µg b.i.d. inhaler starting at Visit 1 (or soon after).

4. Patients with a pre-bronchodilator <math>FEV_1 \geq 50\%</math> and <math>\leq 90\%</math> of the predicted normal value for the patient at the start and end of Run-in (Visits 101 and 199).

• Withholding period of bronchodilators prior to spirometry at Visit 101: SABA for <math>\geq 6</math> hours and FDC or free combinations of ICS/ Long Acting Beta-2 Agonist (LABA) for <math>\geq 48</math> hours, o.d. LABA for at <math>\geq 14</math> days, SAMA for <math>\geq 8</math> hours, LAMA for <math>\geq 7</math> days, xanthines <math>\geq 7</math> days

• One-time re-testing of pre-bronchodilator <math>FEV_1</math> is allowed only at Visit 101. Re-assessment should be done in an ad-hoc visit before randomization.

5. Patients who demonstrate an increase in <math>FEV_1</math> of <math>\geq 12\%</math> within 30 minutes after administration of 400 µg salbutamol/360 µg albuterol (or equivalent dose) at Visit 101. All patients must perform a reversibility test at Visit 101. Use of spacer devices is mandatory. Reversibility may be repeated once.

6. A single parent/legal guardian must be designated to complete all e-Diary entries and attend all clinic visits with the patient.

Key Exclusion criteria	

1. Patients taking a mid-dose ICS (per GINA guidelines) in combination with LABA or any patient taking high-dose ICS.

2. Evidence of unstable disease within 4 weeks prior to Screening (Visit 1).

3. Patients who have had an asthma attack/exacerbation requiring systemic steroids (SCS) or hospitalization or emergency room visit within 3 months prior to Visit 1 (Screening) or more than 3 separate exacerbations in the 12 months preceding Visit 1. If patients experience an asthma attack/exacerbation requiring SCS or hospitalization between Visit 1 and Visit 199 they may be rescreened 3 months after recovery from the exacerbation.

4. Suspected or documented bacterial or viral infection of the upper or lower respiratory tract, sinus or middle ear that is not resolved within 4 weeks of Screening (Visit 1).

5. Prior intubation for asthma

	
6. Patients who, in the opinion of the investigator, are not able to be compliant with study treatments, properly use study drug devices (e.g. DPI, MDI, Concept1, peak flow meter), or who have any medical or mental disorder, situation, or diagnosis which could interfere with the proper completion of the protocol requirements.

Study treatment	

• Indacaterol acetate 75 µg capsules for inhalation, delivered via Concept1

• Indacaterol acetate 150 µg capsules for inhalation, delivered via Concept1

Efficacy assessments	

• Spirometry

• Pediatric ACQ-IA

• Asthma symptoms based on e-Diary

• Peak Expiratory Flow (PEF)

• Rescue Medication Use

Key safety assessments	

• Medical history and physical examination including oropharyngeal examination

• Vital signs

• Hematology, blood chemistry, urine dipsticks

• Electrocardiogram (ECG)

• Adverse events (AEs) including asthma exacerbations, worsening asthma, and serious adverse events (SAEs)

Other assessments	Pharmacokinetic (PK) analysis will be conducted in all patients
Data analysis	
The primary endpoint is change from baseline in pre-dose trough FEV1 (mL) after 2 weeks of treatment. Summary statistics (n, mean, 25th percentile, median, 75th percentile, standard deviation, minimum and maximum) by treatment group will be provided for change from baseline in pre-dose trough FEV1 as well as pre-dose trough FEV1 after 2 weeks of treatment. Inferential testing statistics will not be performed since the sample size is small and power is limited.
 
For secondary endpoints (Spirometry, Pediatric ACQ-IA, Asthma symptoms recorded in e-Diary, Peak Expiratory Flow, Rescue Medication Use), summary statistics will be provided by treatment group.

Key words	indacaterol acetate, asthma, GINA 2015, pediatrics

## 1 Introduction

### 1.1 Background

Asthma is a chronic inflammatory disorder of the airways associated with hyper-responsiveness of airways that leads to recurrent episodes of wheezing, breathlessness, chest tightness, and coughing, particularly at night or in the early morning. These episodes are usually associated with widespread but variable airflow obstruction within the lung that is often reversible either spontaneously or with treatment. Airflow limitation occurs as a result of obstruction or narrowing of the airways when exposed to precipitating factors. Although exacerbations of asthma are episodic, inflammation is chronic ([GINA Global strategy for Asthma management and prevention, 2015](#)). Asthma is defined by its clinical, physiological, and pathobiological characteristics. The wide clinical spectrum of asthma is highly variable, and although different cellular patterns have been observed in asthmatic airways, the presence of airway inflammation remains a consistent feature.

Despite persistent airway inflammation, asthma symptoms are episodic and the relationship between the intensity of inflammation and the severity of asthma is not clearly established. In most patients, the inflammation affects all airways including the upper respiratory tract and nose, but the physiological effects are most pronounced in medium-sized bronchi. Despite the cellular heterogeneity of inflammatory response, the pattern of inflammation in the airways appears to be similar in all clinical forms of asthma at all ages, whether allergic, non-allergic, or aspirin-induced ([GINA 2015](#)).

Asthma most often starts early in life and has variable courses and unstable phenotypes which may progress or remit over time. Despite advances in medical management, childhood asthma continues to be a leading cause of emergency department visits, hospitalizations, and school days missed. Children afflicted with uncontrolled asthma have difficulty exercising, sleeping, and participating in the normal activities of childhood ([Runge and Hill 2009](#)).

Asthma is the most common childhood chronic disease ([Bastain et al 2011](#)) and its prevalence has increased especially among children ([GINA 2014](#)). Children under 18 years represent one-third of all asthmatics according to the MMWR Surveillance summary - National surveillance for asthma 1980 to 2004 (United States) ([Moorman et al 2007](#)), with data showing that the incidence and prevalence of asthma is increasing more rapidly in children than that in adults, particularly in children under 15 years ([Masoli et al 2004](#)).

Due to this high impact of asthma on the quality of life of pediatric patients and caregivers, as well as is costs, several guidelines exist to support clinical care of pediatric asthmatics. Two types of medications are used to treat asthma: long-term control (“prevention”) medications and quick-relief medications, which reverse acute airflow obstruction. All children who have persistent asthma should be started on a long-term control (“prevention”) medication. Such anti-inflammatory medications are taken daily to reduce airway inflammation. The recommended type and dose of long-term control medication depends on the level of asthma severity and the age of the child. For persistent asthma, these guidelines recommend step wise intensification of asthma controller medications. Combinations of different controller medications are recommended as preferred treatment options by various guidelines (NIH, GINA, ICON). Especially fixed dose combinations (FDC) products containing a LABA plus

ICS have been shown to be safe and effective in the management of asthma and recommended by GINA as preferred controller therapy  $\geq$  Step 3 for adult and pediatric population. In older children and adults, ICS/LABA combinations have been shown to improve asthma outcomes to a better extent than higher doses of ICS. ICS/LABA combinations are recommended as the preferred add-on treatment in children  $>5$  years (SIGN, GINA), or  $>12$  years (NAEPP), in other studies they are suggested as an option for children  $>5$  years (AAMH, NAEPP) or at any age (JGPA) ([Woolcock et al 1996](#), [Greening et al 1994](#), [Ducharme et al 2010](#)). However, most of the currently available FDC products (e.g. salmeterol xinafoate/ fluticasone propionate) require twice a day (b.i.d.) dosing to achieve an optimum therapeutic effect in asthma.

Novartis is developing QMF149 which is a fixed-dose combination (FDC) of indacaterol acetate (inhaled LABA with 24 hour duration of action) and mometasone furoate (MF, ICS) for once-daily maintenance treatment of asthma in both adults and children 6 years of age and above. The mono-components are approved medications: indacaterol as the maleate salt for the treatment of chronic obstructive pulmonary disease (COPD) in adults, and MF for the use in asthma in adult and pediatric patients (Asmanex® Twisthaler®).

QMF149 FDC has been used in clinical trials in healthy volunteers, and adult and adolescent asthma patients. Indacaterol acetate has been investigated in healthy volunteers and adult asthma patients and demonstrated a lower incidence of post-inhalation cough compared to indacaterol maleate in asthma patients, while maintaining bronchodilator efficacy, with a very similar safety profile (study CQAB149D2301).

Studies CQMF149E2203 and CQAB149B2357 evaluated indacaterol acetate and maleate, respectively delivered via the Concept1 (Breezhaler®) inhaler in patients with asthma. These two studies support selection of indacaterol dose 150  $\mu$ g once daily in the adult and adolescent population.

A dose-ranging study of indacaterol maleate in adult asthmatic patients demonstrated that a dose of 150  $\mu$ g o.d. was safe and effective (Study CQAB149B2357). The dose of indacaterol acetate was investigated in Study CQMF149E2203 in adult asthma patients, where indacaterol acetate 150  $\mu$ g and 75  $\mu$ g was delivered via Concept1 compared to placebo. The study demonstrated that both 150  $\mu$ g and 75  $\mu$ g doses were found to be superior to placebo and indacaterol acetate 150  $\mu$ g showed positive trends in terms of trough forced expiratory volume in 1 second (FEV1), peak expiratory flow (PEF), and rescue medication use compared with indacaterol acetate 75  $\mu$ g.

This study is part of the pediatric development plan for QVM149 and is designed based on agreement with EU Pediatric Committee (PDCO). Prior to progressing into Phase III testing of QMF149 in  $\geq 6$ ,  $<12$ -year-old children, a dose selection study of indacaterol in this population is needed. The objective of the study is to assess the benefit of two doses of indacaterol when added to baseline ICS therapy to identify an appropriate dose to carry forward for Phase III evaluation. This will be achieved by assessing the totality of lung function data, symptoms and systemic exposure to indacaterol in 6 to 11-year-old children compared with historical PK data collected in adults.

## 1.2 Purpose

This study is designed to explore lung function effects of two doses of indacaterol acetate, 75 µg and 150 µg, in pediatric asthma patients 6-11 years old, and to compare the systemic exposure to indacaterol in plasma with historical data in adults, to identify an appropriate dose to Phase III evaluation.

## 2 Study objectives and endpoints

### 2.1 Primary objective(s)

To evaluate indacaterol acetate 75 µg o.d and 150 µg o.d. in terms of change from baseline in pre-dose trough FEV1 after 2 weeks of treatment.

### 2.2 Secondary objective(s)

- To evaluate the systemic exposure to indacaterol in plasma following sparse pharmacokinetic (PK) sampling on Day 1 and Day 14 after oral inhalation of indacaterol acetate 75 µg and 150 µg
- To evaluate the clinical effects and pharmacodynamics of indacaterol acetate (75 µg and 150 µg o.d.) after 2 weeks of treatment in terms of:
  - Pediatric interviewer-administered Asthma Control Questionnaire (ACQ-IA) score at Week 2
  - FEV1 and forced vital capacity (FVC) rate at 30 minutes and 1-hour post dose at Week 2
  - Rescue medication usage over 2 weeks of treatment as determined by patient diary data
  - Symptoms as recorded by patient e-diary
  - Pre-dose morning and evening peak expiratory flow (PEF) over 2 weeks of treatment as determined by electronic peak flow meter data.
- To evaluate the safety (including labs, vital signs, ECG, adverse events), and tolerability of indacaterol acetate (75 and 150 µg o.d.) over 2 weeks of treatment.

### 2.3 Exploratory objectives

Not applicable

## 3 Investigational plan

### 3.1 Study design

This study uses a randomized, multicenter, double-blind, active-controlled study design. The primary endpoint will be evaluated after 2 weeks of treatment with indacaterol acetate as change from baseline in children ≥6 years and <12 years (GINA step 2 & 3). Study treatment will be administered on top of background asthma ICS controller therapy (fluticasone propionate 100 µg b.i.d. or dose equivalent). This study will consist of 4 epochs: Screening, Run-in, Treatment, and Follow-up (telephone contact for safety).

## Screening (Visit 1)

At an initial Screening visit (Visit 1) informed consent is obtained from the parent(s)/legal guardian(s). Additionally, a patient assent is obtained before any study-related assessments or procedures are performed (according to locally accepted policy/practice). Patients will be screened to determine eligibility (Section 4.1 and 4.2). Where appropriate, concomitant medications are adjusted at this visit and washout begins for any prohibited medications. The window between Visit 1 and 101 (Screening Epoch) is to complete all Screening measures and to washout prohibited medications (Table 5-1, Table 5-2 and Table 5-3). It can be as short as necessary and last up to 30 days.

Patients meeting Screening eligibility will receive the following at the Screening visit (Visit 1):

- Fluticasone propionate 100 µg b.i.d. delivered via Diskus®/ Accuhaler® (if not available in a specific country, fluticasone propionate 125 µg b.i.d. via MDI inhaler; if these formulations are not available, then the closest equivalent to fluticasone propionate 100 µg b.i.d. should be given; MDI can be used with spacer).

The child's parent/ legal guardian will be instructed that their child discontinue their current ICS and be placed on fluticasone propionate. If their child has already taken his/ her ICS prior to arriving at the site, then the child should begin using the provided fluticasone inhaler the next day. Patients will be instructed to take their fluticasone inhaler daily in the morning and evening, in place of their previous ICS.

- The patient's parent/ legal guardian must be instructed that the patient should NOT take fluticasone on the mornings before arriving at the site for their study visits. They will take their morning fluticasone dose at the site on those days. Therefore, it is important that they bring the fluticasone inhaler with them to every study visit. If it is found that a patient did take the fluticasone morning dose prior to arriving at the site, this should be documented in the patient's source and the visit will go on as scheduled.
- Patients will receive the short acting β2-agonist (SABA) salbutamol/albuterol to use as rescue medication throughout the study. Parents/ legal guardians must be instructed that their child NOT take rescue salbutamol/albuterol for at least 6 hours prior to any of their study visits (unless they are experiencing symptoms that mandate salbutamol/albuterol inhalation, in which case the visit would be re-scheduled). Spacers are allowed for the rescue medication use. No other rescue medication is allowed in the study.
- Patients/ patient's parent/legal guardian will be issued an electronic diary (e-Diary) to record asthma symptoms and rescue medication use, which will be completed by the patient's parent/legal guardian. The patient's parent/legal guardian will be instructed to bring the e-Diary with them to every study visit.
  - Patients will also be issued an electronic Peak Flow meter (part of e-Diary) to record their Peak Expiratory Flow (PEF) rate. The patient and his/her parent/legal guardian will be instructed on how to use this device.
  - Patients are allowed to use a spacer while taking their inhaled medication and must use a spacer for reversibility testing.

Visit 1 should be conducted up to 30 days before Visit 101. Visit 1 and 101 may occur on the same day, as long as no washout is required (no short-acting rescue medication taken within 6 hours, and appropriate washout of prohibited treatment in [Table 5-1](#), [Table 5-2](#) and [Table 5-3](#)).

Patients should bring their ICS (fluticasone propionate) inhaler, rescue salbutamol/albuterol, PEF and e-Diary, and all study medications with them to every study visit.

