#### **5.5.3.2 Handling of additional treatment**

The following non-study drug will be monitored as follows:

The non-study drug must be received by a designated person at the study site, handled and stored safely and properly, and kept in a secured location to which only the investigator and designees have access. Clinical supplies are to be dispensed only in accordance with the protocol.

The investigator must maintain an accurate record of the shipment and dispensing of the non-study drug in a drug accountability log. Monitoring of drug accountability will be performed by monitors during site visits or remotely and at the completion of the trial. Patients will be asked to return all unused non-study drug and packaging at the end of the Run-in for the Run-in medication and at the end of the study or at the time of discontinuation of study drug for the rescue medication.

These medications are:

- Salbutamol (100 µg) or albuterol (90 µg) used as rescue medication from Visit 1 to Visit 299
- Fluticasone propionate (100 µg b.i.d. or acceptable dose equivalent as outlined in [Section 3.1](#) used as Background medication from Visit 1 to Visit 299

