### **5.5.6 Rescue medication**

At Visit 1 (Screening), all patients will be provided with a short acting  $\beta_2$ -agonist (100  $\mu$ g salbutamol/90  $\mu$ g albuterol via inhaler) which they will be instructed to use throughout the study as rescue medication. Nebulized salbutamol is not allowed as rescue medication throughout the entire trial. No other rescue treatment is permitted.

In order to standardize measurements, patients will be instructed to abstain from taking rescue medication (salbutamol) within 6 hours of the start of each visit where spirometry is being performed unless absolutely necessary. If rescue medication is taken within 6 hours prior to spirometry assessments, then the visit should be rescheduled to the next day if possible and the number of puffs of rescue medication taken recorded in the patient e-Diary.

Additionally, patients will be provided with fluticasone propionate 100  $\mu$ g (or dose equivalent see Section 5.1.2) via an inhaler, which should be taken b.i.d. beginning at Visit 1, or the next day if patient already took their daily ICS, and continue through the duration of the trial. If the patient is currently taking an ICS (with or without additional controller medication) the patient must switch to fluticasone provided at this visit. Fluticasone should be taken in the morning, prior to study drug, and in the evening. On days of study visits, patients should bring their fluticasone inhaler with them and take the dose at the site under supervision of study staff. Fluticasone use should also be captured in the eCRF.

The rescue salbutamol/albuterol and fluticasone will be provided to the patients by the study center and reimbursed locally by Novartis.

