**Table 5-1 Prohibited asthma-related medications**

Class of medication	Minimum washout period starting at Visit 101 
Long-acting β2 agonists (LABA)	LABAs used b.i.d. must be discontinued 48 hours prior to Visit 101. LABAs used o.d. must be discontinued at least 14 days prior to Visit 101).
Long Acting Muscarinic Antagonist (LAMA)	Must be discontinued 7 days prior to Visit 101.
Short acting anticholinergics (SAMA)	Must be discontinued 8 hours prior to Visit 101.
Fixed combinations of short-acting β2-agonist and short-acting anticholinergics	Must be discontinued 8 hours prior to Visit 101.
Salbutamol/albuterol (SABA) provided at Visit 1 and throughout study as required for rescue medication	Must be withheld 6 hours prior to study visits beginning at Visit 101.
Short acting β2-agonists (SABAs) (other than Salbutamol/albuterol provided at Visit 1 for rescue medication)	Must be discontinued at Visit 1 and are not permitted during the study 
Intra-muscular depot corticosteroids	Must be discontinued 3 months prior to Run-in (Visit 101)
Systemic corticosteroids (Parenteral or oral)	Must be discontinued 3 months prior to Run-in (Visit 101)
Immunoglobulin E inhibitors (e.g. omalizumab)	Must be discontinued 6 months prior to Run-in (Visit 101)
Xanthines	Must be discontinued 7 days prior to Run-in (Visit 101)
Systemic mast cell stabilizers (e.g. cromoglycate, nedocromil, ketotifen)	Must be discontinued 7 days prior to Run-in (Visit 101)

 This table is not considered all-inclusive. Medications should be assessed for adherence to the indication and other inclusion/exclusion criteria.

 These medications are also prohibited if administered for other indications.

 SABA (salbutamol/albuterol rescue medication) should be withheld for at least 6 hours prior to spirometry measurements at clinic visits if possible. Clinic visits may be rescheduled if rescue medication were taken less than 6 hours prior to the spirometry assessments.

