## **5.6 Study completion and discontinuation**

### **5.6.1 Study completion and post-study treatment**

Completion of the study will be when the last patient has completed Visit 301 and as close as possible to serious adverse event (SAE) Follow-up at Day 44.

The investigator must provide Follow-up medical care for all patients who are prematurely withdrawn from the study, or must refer them for appropriate ongoing care.

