- Clinically significant abnormal laboratory value(s) (e.g., potassium below 3.0 mmol/L, LFT >3 x ULN)
- Any other protocol deviation that results in a significant risk to the patient's safety

If discontinuation of study treatment occurs, the patient should NOT be considered withdrawn from the study. The patient should return to the clinic as soon as possible, after discontinuation of study drug, for a study treatment discontinuation visit (Visit 299 will act as an early discontinuation visit in this case) and directly move into the Follow-up epoch.

Treatment discontinuation visit assessments detailed in the [Table 6-1](#) should be completed and recorded in the eCRF. The investigator must determine the primary reason for the patient's premature discontinuation of study treatment and record this in the End of treatment disposition page in the eCRF.

The investigator must also contact the IRT to register the patient's discontinuation from study treatment.

The data which must continue to be collected for all patients (including the patients discontinuing study treatment) are adverse event and serious adverse events for up to 30 days after drug discontinuation until the end of the study Follow-up visit (Visit 301).

Documentation of attempts to contact the patient should be recorded in the source documentation.

If study drug discontinuation occurs because treatment code has been broken, please refer to [Section 5.5.9](#).

If the patient fails to return for an end of study visit for unknown reasons, every effort should be made to contact them as specified in [Section 5.6.4](#).

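### The supplied reliever is the only one allowed for the whole study, yet its stated use ends at Visit 299 and early stoppers must return it before Follow-up

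*Protocol*

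**What the plan says.** **Supply and ban.** Section 3.1, Screening (Visit 1), issues salbutamol/albuterol "to use as rescue medication throughout the study" and continues: "No other rescue medication is allowed in the study". Section 5.1.2 repeats the supply for the same span. Section 5.5.6 says "No other rescue treatment is permitted" and also excludes nebulized salbutamol for the whole trial. For short-acting beta-agonists other than the inhaler provided at Visit 1, Table 5-1 says: "Must be discontinued at Visit 1 and are not permitted during the study".

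**Period of use and return.** Section 5.5.3.2 lists the same inhaler as "used as rescue medication from Visit 1 to Visit 299". It asks patients to return what is unused "at the end of the study or at the time of discontinuation of study drug for the rescue medication".

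**Extent of the study.** Section 3.1 counts Follow-up as one of four epochs, and Section 6 gives it 30 days after the last treatment. Section 5.6.1 says: "Completion of the study will be when the last patient has completed Visit 301". After study drug is stopped early, Section 5.6.2 says that "the patient should NOT be considered withdrawn from the study"; the child attends Visit 299 as a discontinuation visit and goes directly into Follow-up.

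**The concern.** The ban on other relievers and the availability of the one permitted reliever are given different time spans. Where the ban outlasts the supply, a child is in the study with no reliever that the text allows.

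This matters most for children who stop study drug early. The mandatory reasons in Section 5.6.2 include worsening asthma, excessive rescue use, a fall in PEF, and moderate or severe exacerbation. The children to whom the return rule applies most plainly therefore include those most likely to need a reliever. Section 6.5.7 adds that patients may not treat themselves for worsening or exacerbation with anything other than the rescue medication.

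Sites would also have to resolve the conflict for themselves, and may do so differently. Asthma events reported in Follow-up could then partly reflect whether the inhaler was left with the child, which makes the safety data a little harder to read.

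**Working it through.** This is a comparison of texts; the only arithmetic concerns the length of Follow-up and the planned number of non-completers.

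1. **Length of Follow-up.** Table 6-1 puts Visit 299 at Day 14 and Visit 301 at Day 44. 44 − 14 = 30 days, which reproduces the length in Section 6. For an early stopper, Section 3.1 places the telephone call 30 days after the last treatment date, so the interval after the inhaler is returned is at most 30 days from the last dose.

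2. **Planned non-completers.** Section 9.7 assumes about 10% of 80 randomized patients: 0.10 × 80 = 8, and 80 − 8 = 72, the evaluable number given there.

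3. **Children who stop study drug early.**
   - Return of the reliever: at discontinuation of study drug (Section 5.5.3.2).
   - Status: not withdrawn, moved into Follow-up (Section 5.6.2).
   - Ban on other relievers: covers the study (Sections 3.1 and 5.5.6, Table 5-1).
   - Release from the ban, or a reliever named for Follow-up: none found.
   - Result: the ban applies and the permitted product has been returned. This does not depend on how the end of the study is defined for completers, because Section 5.6.2 says outright that these children are still in the study.

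4. **Completers.** The document uses the end of the study in two senses. Sections 6.4.4 and 6.5.5 attach the label to Visit 299; Section 5.6.1 places completion at Visit 301.
   - If the study ends at Visit 299, then supply, use period, ban and return all end together and there is no gap.
   - If it ends at Visit 301, then supply, ban and return all run to Visit 301, and only the Visit 299 limit in Section 5.5.3.2 disagrees.
   - A ban without supply arises only if the later end is used for the ban and the earlier one for the return or the use limit.
   - Result: an inconsistency in the stated period, not an instruction to remove the inhaler.

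5. **Assessment schedule.** Table 6-1 issues rescue medication at Visits 1, 101, 199 and 201. It collects unused study medication at Visit 299 but has no row for collecting rescue medication. Visit 301 is a telephone contact, and the text does not say how an inhaler would be returned then.

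6. **Reach into the safety analysis.** Section 9.5.2 counts non-serious AEs as treatment-emergent up to 7 days after the last inhalation and SAEs up to 30 days. Any effect on the treatment-emergent summaries is therefore limited mainly to those windows.

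**The case against.** The strongest reply is that the text does not leave all children without a reliever. A reader might infer that each of the roughly 80 children hands back the inhaler at Visit 299 and has nothing permitted for 30 days. The protocol does not say so: return is due at the end of the study, which Section 5.6.1 places at Visit 301, and no row of Table 6-1 collects rescue medication. The use limit, the Visit 299 labels and the telephone format of Visit 301 make that reading possible, but it remains a reading. This part of the reply stands.

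Second, care is provided for elsewhere. Section 6.5.6 has worsening asthma evaluated and treated as the investigator sees fit, with site staff monitoring until control returns. Section 7.1 requires AEs to be treated appropriately, including with concomitant medication. In addition, the sanction for prohibited medication in Section 5.6.2 is to stop study drug, which has no force once the drug has stopped. These points make it unlikely that a site would leave a child untreated. They soften the practical effect, but a site relying on them would be departing from the written ban, so they do not reconcile the sections. The follow-up care duty in Section 5.6.1 is worded for patients withdrawn from the study, which Section 5.6.2 says early stoppers are not.

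Third, the 10% in Section 9.7 is not a count of children who stop drug and enter Follow-up. It can include withdrawals of consent and losses to follow-up. That is correct.

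Fourth, the consequence for AE interpretation is small: the 7-day window excludes most of Follow-up for non-serious events, the same rule applies in both arms, and the primary endpoint is measured before Follow-up. That is also correct.

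**Conclusion.** The point holds as an internal inconsistency. For children who stop study drug early, the stated rules contradict each other: return of the only permitted reliever, continued membership of the study, and no release from the ban. For completers, the contradiction is confined to the period of use, whole study against Visit 299, and comes from the two meanings given to the end of the study.

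The interval concerned is at most 30 days after the last dose. The number of children is not stated; 8 of 80 is at most a rough upper guide, and only if non-completion turns out as assumed. The absence of a permitted reliever is a literal consequence of reading the sections together. A reader might take it as an intention of the protocol, but nothing in the text supports that. The effect on the safety summaries is minor. The reason to act is that the explicit conflict falls on a group that includes children with deteriorating asthma.

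**What to change.** Reconcile Sections 3.1, 5.1.2 and 5.5.6 and Table 5-1 with Sections 5.5.3.2, 5.6.1 and 5.6.2. State to which epochs the reliever supply applies and to which epochs the ban on other relievers applies, so that no epoch carries the ban without the supply. Give one return point for the inhaler that fits the Follow-up epoch, for completers and for early stoppers, and use the end of the study in one sense. What the rule should be clinically is for the sponsor's clinical team to decide.

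The cost is wording in an amendment and the matching site instructions, and possibly later return of some inhalers. No analysis or sample size changes.
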